2.1 Primary Objective

We aim to assess if a TTS fentanyl-based sedation protocol is at least non-inferior when compared to a totally intravenous remifentanil infusion protocol. To do that, we will compare the global work of breathing (WOB) of the patients randomized to receive TTS-fentanyl vs. remifentanil alone.

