Impact of TOtally transdErmal Sedation in the weaning from remifentanil infusion among critically ill patients undergoing mechanical ventilation: a pilot randomized-controlled Study (The TOES Trial)

NCT04204967

24/02/2020 versione n°3

Abstract

Rationale and Background: The choice of the sedation protocol has a massive impact on the duration of mechanical ventilation and the timing of extubation. Many sedation protocols are described in the literature. No data are available about the possibility of using TTS-fentanyl as an alternative to intravenous opioids during the weaning phase from mechanical ventilation and the post-extubation period until the discharge from ICU to the ward. **Objective:** We aim to assess if a TTS fentanyl-based sedation protocol can have an impact on the global Work of Breathing (WOB). Secondary endpoints of the study are the duration of mechanical ventilation, the duration of continuous infusion of opioids, the length of stay in ICU and in hospital. **Methods:** We will perform a 2-arm, single-center, prospective randomized controlled trial. The duration of the study will be approximately one year, for a total of 24 patients. Patients ventilated in pressure support ventilation (PSV) receiving continuous intravenous remifentanil for more than 5 days will be considered eligible. Eligible patients will be randomized in 2 groups: Group 1 will receive remifentanil; Group 2 will receive TTS-fentanyl and remifentanil. Patients will be selected from the population admitted to the adult ICU (a 20-beds unit), the post-operative ICU (a 13-beds unit), and the NeuroICU (a 10-beds unit). An Edi Catheter for diaphragm electrical activity monitoring will be put in place for each patient. **Outcomes:** The primary endpoint is to demonstrate that the area under the curve (AUC) of the work of breathing per minute in the intervention group is not higher than the control group. Secondary endpoints are differences respiratory rate, tidal volume, arterial blood pressure, heart rate, global duration of mechanical ventilation and opioids infusion, length of stay in ICU and in hospital. **Statistical Analysis:** Distribution normality will be assessed with the Kolmogorov-Smirnov test. Continuous variables will be reported expressed as medians (interquartile ranges). Qualitative variables will be reported as frequencies. Analysis on the primary efficacy criterion and other quantitative variables will be assessed with the Wilcoxon-Mann-Whitney test. Categorical outcomes will be compared with the chi-square test, or Fisher's exact test, as appropriate. Cochran-Mantel-Haenszel statistics will be reported for all these results. Two-way analysis of variance (ANOVA) for repeated measures with Bonferroni correction will be used to determine the differences in secondary endpoints. Comparisons between groups regarding these variables at each study time point were performed with the Student's t-test or Mann-Whitney test, as appropriate. Mean difference and 95% confidence interval [CI95%] are reported for most significant results. Two-tail p values≤0.05 Will be considered significant.

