Exclusion criteria	
 • Hypoxemic respiratory failure ($P/F < 200$ mmHg); • Haemodynamic instability requiring high doses of inotropes or vasopressors; • Current enrollment or plan to enroll in any interventional clinical study in which an investigational treatment or approved therapy for investigational use is administered within 30 days or 5 half-lives of the agent, prior to the baseline visit; • Any condition that may contraindicate the use of remifentanil or transdermal fentanyl; • Patient admitted for post-operative monitoring after elective surgery; • EAdi catheter contraindicated. • Hypersensitivity to the active substance or any of the excipients; • Hepatic or renal impairment; • Fever (body temperature ≥ 38 °C) or septic shock, hypothermia (body temperature < 35 °C) or presence of active surface cooling systems; • Hypercapnic patients with a $PaCO_2 > 45$ mmHg; • Delirium state defined as RASS ≥ 3 and CAM-ICU positive; • Patients with a BMI ≥ 35.
Primary Objective	To assess if a transdermal fentanyl-based sedation protocol is at least non-inferior when compared to a totally intravenous remifentanil infusion protocol. we will compare the global work of breathing (WOB) of the patients randomized to receive transdermal fentanyl vs. remifentanil alone. We will calculate the area under the curve (AUC) of the work of breathing per minute in the intervention group vs the control group
Secondary Objectives	Main secondary endpoints include differences in respiratory rate, tidal volume, arterial blood pressure, heart rate, global duration of mechanical ventilation, length of stay in ICU and in hospital.
Number of Patients	N = 24

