Statistical Analysis	
Distribution normality will be assessed with the Kolmogorov-Smirnov test. Continuous variables will be reported expressed as medians (interquartile ranges). Qualitative variables will be reported as frequencies. Analysis on the primary efficacy criterion (AUC of the work of breathing) and other quantitative variables will be assessed with the Wilcoxon-Mann-Whitney sum of rank test. Categorical outcomes will be compared with the chisquare test, or Fisher's exact test, as appropriate: Cochran-Mantel-Haenszel statistics will be reported for all these results. Two-way analysis of variance (ANOVA) for repeated measures with Bonferroni correction will be used to determine the differences in work of breathing per breath, inspiratory effort, delta EAdi, plateau pressure, P 0.1 respiratory rate, tidal volume, arterial blood pressure, heart rate in the two groups. Comparisons between groups regarding these variables at each study timepoint were performed with the Student's t test or Mann-Whitney test, as appropriate. Mean difference and 95% confidence interval [CI95%] are reported for most significant results. Two-tail p values≤0.05 Will be considered significant. Statistical analysis will be performed with SPSS software package (SPSS Inc. Released 2009. PASW Statistics for Windows, Version 18.0. Chicago: SPSS Inc.).

-----------------------------	---

1. Rationale and Background

Invasive mechanical ventilation is a lifesaving intervention among critically ill patients. However, prolonged ventilation is associated with increased morbidity and mortality. Optimal processes for weaning from ventilation have been studied for many years and have led to evidence-based clinical practice guidelines to facilitate early liberation from invasive mechanical ventilation. It is crucial to avoid prolonged MV, and weaning from the mechanical ventilator should not be delayed to avoid complications as VAP, weakness and atrophy of respiratory muscles, and the need for a tracheostomy (Jeong et al. 2015; Béduneau et al. 2017; Girard et al. 2017; Peñuelas et al. 2011; Perkins et al. 2018).

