2.2 Primary Endpoint

To demonstrate that the area under the curve (AUC) of the work of breathing per minute (assessed at 1, 6, 12, 24 hours for the first day after randomization, and every 24 hours for the following days) in the intervention group is not higher than the control group. We will also analyze differences in work of breathing per breath, inspiratory effort, delta EAdi, plateau pressure, driving pressure, transpulmonary driving pressure, pulmonary compliance, P0.1, P/F ratio.

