36 hours* (visit 8)	ABG sample, respiratory and hemodynamic parameters, GCS, RASS, dosage of remifentanil and TTS-fentanyl
42 hours* (visit 9)	ABG sample, respiratory and hemodynamic parameters, GCS, RASS, dosage of remifentanil and TTS-fentanyl
48 hours* (visit 10)	ABG sample, respiratory and hemodynamic parameters, GCS, RASS, dosage of remifentanil and TTS-fentanyl, Recording of EAdi, flow, and Paw
54 hours* (visit 11)	ABG sample, respiratory and hemodynamic parameters, GCS, RASS, dosage of remifentanil and TTS-fentanyl
60 hours* (visit 12)	ABG sample, respiratory and hemodynamic parameters, GCS, RASS, dosage of remifentanil and TTS-fentanyl
66 hours* (visit 13)	ABG sample, respiratory and hemodynamic parameters, GCS, RASS, dosage of remifentanil and TTS-fentanyl
72 hours* (visit 14)	ABG sample, respiratory and hemodynamic parameters, GCS, RASS, dosage of remifentanil and TTS-fentanyl, Recording of EAdi, flow, and Paw
End of observation period for the primary endpoint	72 hours after randomization

Treatment suspended	The treatment duration will be dependent on the subject's clinical course and the investigator's judgment on the perceived need to continue the study drug
Safety FU period	Permanent discontinuation of TTS-fentanyl: start of 24 hours of Safety Follow up Period (any adverse event will be recorded on the CRF)
End of Study Visit	This visit occurs at the discharge from the ICU or in case of death after the observation period for the primary endpoint ABG sample, respiratory and hemodynamic parameters, GCS, RASS, Data on the global duration of opioid therapy/length of stay (LOS) in hospital and ICU

*Hours from randomization

Table 1. Study visits and assessments

6. Statistical analysis

Distribution normality will be assessed with the Kolmogorov-Smirnov test. Continuous variables will be reported expressed as medians (interquartile ranges). Qualitative variables will be reported as frequencies.

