Analysis of the primary efficacy criterion (AUC of the work of breathing) and other quantitative variables will be assessed with the Wilcoxon-Mann-Whitney sum of rank test. Categorical outcomes will be compared with the chi-square test, or Fisher's exact test, as appropriate: Cochran-Mantel-Haenszel statistics will be reported for all these results. Two-way analysis of variance (ANOVA) for repeated measures with Bonferroni correction will be used to determine the differences in work of breathing per breath, inspiratory effort, delta EAdi, plateau pressure, P 0.1 respiratory rate, tidal volume, arterial blood pressure, heart rate in the two groups. Comparisons between groups regarding these variables at each study time point will be performed with the Student's t-test or Mann-Whitney test, as appropriate. Mean difference and 95% confidence interval [CI95%] are reported for most significant results.

Two-tail p values≤0.05 Will be considered significant. Statistical analysis will be performed with SPSS software package (SPSS Inc. Released 2009. PASW Statistics for Windows, Version 18.0. Chicago: SPSS Inc.).

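### The primary aim is non-inferiority on work of breathing, but the plan has no margin or decision rule and tests only for a difference

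*Combined protocol and SAP*

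**What the plan says.** - **Objective.** Section 2.1 reads: "We aim to assess if a TTS fentanyl-based sedation protocol is at least non-inferior when compared to a totally intravenous remifentanil infusion protocol". The synopsis says the same. The abstract's objective differs: it asks whether the patch protocol affects work of breathing, which is a question about a difference in either direction.
- **Endpoint.** The abstract says "The primary endpoint is to demonstrate that the area under the curve (AUC) of the work of breathing per minute" is not higher on the patch. Sections 2.2 and 6.1 use the same success wording, that the AUC "in the intervention group is not higher than the control group", and attach no quantity to it.
- **Analysis.** Section 6 states that the "primary efficacy criterion (AUC of the work of breathing) and other quantitative variables will be assessed with the Wilcoxon-Mann-Whitney sum of rank test", and that "Two-tail p values≤0.05 Will be considered significant". The abstract and synopsis agree.
- **Estimates.** Section 6 summarises continuous variables as medians with interquartile ranges. It limits mean differences with 95% confidence intervals to the results it calls most significant.
- **Sample size.** Section 6.1 sets 12 per group, based on earlier physiological studies of 10 patients, attrition below 10% and a pilot rule of thumb. It gives no margin, SD, effect size or power, and says that work-of-breathing data in this setting are lacking.

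**The concern.** A non-inferiority claim says that any worsening is smaller than a stated amount. It needs that amount, and a rule that compares a confidence limit with it. The plan has neither. The null hypothesis of the planned test is no difference, and failing to reject that null is not evidence for it.

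The plan therefore has one valid route to its claim, a significantly lower AUC on the patch. If the arms are similar, which is all that non-inferiority requires, the result will usually be p>0.05. The plan does not say how that would be read, and the endpoint wording invites the reading that the patch has been shown to be no worse. A confidence interval for the difference would at least show what had been excluded, but none is assured for a null primary result.

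**Working it through.** **1. The plan's own figure.** Taking the 10 patients of section 6.1 as per group (the text does not say so) and attrition at its 10% upper bound: 10/(1 − 0.10) = 11.1, rounded up to 12, and 2 × 12 = 24. The sample size reproduces, but it uses no margin, SD or power and so has no link to a non-inferiority claim.

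**2. Assumptions for the rest.** The documents give no SD for the AUC, so effects and margins are in SD units. I assume normal data, equal SDs and the exact two-sided 5% Wilcoxon-Mann-Whitney test. With 12 per arm the patch arm is significantly higher when the smaller U is at most 37 in that direction (exact one-sided probability 0.0225). The cut-offs are 30 for 11 per arm (0.0237) and 23 for 10 per arm (0.0216).

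**3. How often a true worsening is missed.** Chance of not finding the patch arm significantly higher, from 100,000 simulated trials per setting:

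| True worsening | 12 per arm | 11 per arm | 10 per arm |
|---|---|---|---|
| 0.5 SD | 81% | 82% | 84% |
| 0.8 SD | 57% | 60% | 65% |
| 0.9 SD | 48% | 51% | 57% |
| 1.0 SD | 40% | 43% | 49% |

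With 12 per arm, a worsening is missed more often than found up to about 0.85 to 0.9 SD. Attrition of 10% would leave 12 × 0.9 = 10.8, so 11 per arm is closest to the plan's assumption. Ten per arm is a stress case (2/12 = 17% loss).

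**4. The one valid route.** If the arms are truly equal, the patch arm is significantly lower in 2.2% of simulated trials with 12 per arm, in line with the exact 0.0225.

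**5. Precision.** The half-width of a t-based 95% interval is t(0.975, 2n − 2) × √(2/n) SD.
- n = 12: 2.074 × 0.408 = 0.85 SD
- n = 11: 0.89 SD
- n = 10: 0.94 SD

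The Hodges-Lehmann interval for 12 per arm runs from the 38th smallest to the 38th largest of the 12 × 12 = 144 pairwise differences. Its exact coverage is 1 − 2 × 0.0225 = 95.5%, and its mean half-width is 0.88 SD (20,000 runs).

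**6. Power if a margin were set.** These figures are t-based, with true difference zero and one-sided 2.5%. Power = 1 − F(t(0.975, 2n − 2)), where F is the noncentral t distribution with 2n − 2 degrees of freedom and noncentrality m/√(2/n), for margin m in SD units. With n = 12:
- m = 0.5: noncentrality 0.5/0.408 = 1.22, power 22%
- m = 0.8: 1.96, power 47%
- m = 1.0: 2.45, power 65%
- 80% power needs m = 1.20 (1.26 with 11 per arm, 1.33 with 10)

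Conversely, the per-arm size for 80% power is n = 2(1.96 + 0.84)²/m². This gives 63 at 0.5 SD, 25 at 0.8 SD and 16 at 1.0 SD, before attrition.

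**The case against.** The strongest reply is that this is a phase II pilot whose size rests on precedent, that section 6.1 admits prior data are lacking, and that nowhere does the plan say p>0.05 will be taken as non-inferiority. The harm is then a possible misreading rather than a stated rule. The abstract's objective is a two-sided question, which the planned test fits. The phrase limiting confidence intervals could mean the most important results, which would naturally include the primary endpoint. All the figures above are in SD units under normality, although the plan itself uses medians and a rank test.

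Part of this stands. A small sample is defensible in a pilot, and the point here does not ask for more patients. The objective is worded inconsistently, not uniformly as non-inferiority. The figures depend on the stated assumptions.

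It does not remove the mismatch. Section 2.1 and the synopsis say non-inferior outright, and the endpoint is written as something to be demonstrated. A plan that states such a claim must say what result would support it. On either reading, the phrase about confidence intervals does not guarantee one for a null primary result, and a mean difference does not correspond to a rank test.

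**Conclusion.** The concern holds and needs correcting. As written, the analysis cannot support the primary conclusion when the arms are similar. This is a conflict between claim and analysis, not a missing detail, and it does not depend on any assumed SD.

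The size does depend on assumptions (normal AUC, equal SDs, effects in SD units). On those, an interval centred on zero with 12 per arm would leave a worsening of about 0.85 SD unexcluded, and formal non-inferiority is realistic only for a margin of about 1.2 SD. Because prior data are lacking, the between-arm estimate and its precision are the most useful things this pilot can supply, and the plan does not guarantee them.

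**What to change.** Amend sections 2.1, 2.2, 6 and 6.1 and the matching abstract and synopsis text so that they all state one aim.

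1. **Preferred.** Restate the primary objective as: *to estimate the between-arm difference in the AUC of work of breathing per minute through 72 hours, with a two-sided 95% confidence interval*. Use the Hodges-Lehmann shift and its interval, which match the rank test. Add: *p>0.05 will not be read as not higher or non-inferior*.
2. **Only if non-inferiority is kept.** Fix and justify a margin in advance, and claim non-inferiority only if the upper limit of the two-sided 95% interval lies below it. The documents describe no blinding, so the margin should be set before enrolment. Analysis sets would also need defining, including how deaths within 72 hours, which section 7 counts as withdrawals, are handled. With 12 per arm this is realistic only for a very wide margin.
3. **In either case.** Report the estimate and interval for the primary endpoint regardless of significance, and preferably for the listed secondary endpoints too, in place of the present limit to the most significant results.

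Option 1 and item 3 change wording only, with no new patients or measurements; the cost is a more modest claim. Option 2 costs more: it needs a margin that the admitted lack of data makes hard to justify, and about 25 to 63 patients per arm for margins of 0.8 to 0.5 SD.

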2.2 Primary Endpoint

To demonstrate that the area under the curve (AUC) of the work of breathing per minute (assessed at 1, 6, 12, 24 hours for the first day after randomization, and every 24 hours for the following days) in the intervention group is not higher than the control group. We will also analyze differences in work of breathing per breath, inspiratory effort, delta EAdi, plateau pressure, driving pressure, transpulmonary driving pressure, pulmonary compliance, P0.1, P/F ratio.

2.3 Secondary Objectives

Secondly, we will assess if a TTS fentanyl-based sedation protocol can have an impact on the duration of mechanical ventilation, as well the duration of continuous infusion of opioids, the length of stay in ICU and hospital compared to a totally intravenous remifentanil infusion protocol.

2.4 Secondary Endpoints

We will analyze differences in respiratory rate, tidal volume, arterial blood pressure, heart rate, global duration of mechanical ventilation and intravenous remifentanil infusion, length of stay in ICU and in hospital.

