to intravenous opioids during the weaning phase from mechanical ventilation and the post-extubation period until the discharge from ICU to the ward. There is only a case-report documenting the use with success of TTS-fentanyl for a patient who developed central hyperventilation(Adachi et al. 2007).

Our hypothesis is that, due to the intrinsic pharmacokinetics and pharmacodynamic characteristics of TTS formulation of fentanyl, it can have a role in weaning the patient from intravenous opioids, such as remifentanil, and mechanical ventilation, reducing the duration of MV itself. It can have also an impact on costs allowing the discharge to the ward of patients with an ongoing patch.

2. Study Objectives and Endpoints

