4.2 Treatment Period

The treatment period starts immediately with the baseline assessments.

In Group 1, in which remifentanil infusion is administered alone, the infusion rate will be increased or decreased according to the study protocol based on PaCO₂ value resulting from the Arterial Blood Gases sample (ABG) collected at each visit.

In Group 2, TTS-fentanyl will be administered with a starting dose of 50 mcg/hr simultaneously with the preexistent remifentanil continue infusion. Remifentanil infusion rate will be increased or decreased based on PaCO₂ value resulting from the Arterial Blood Gases sample (ABG) collected at each visit. After randomization, the TTS-fentanyl dose can be modified every 24 hours according to the study protocol to achieve the desired effect in terms of PaCO₂ value resulting from the Arterial Blood Gases sample (ABG) collected.

A priori we will no exceed 0,2 mcg/kg/min for remifentanil infusion in both arms.

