5.4 Reporting of previous/concomitant therapy in the CRF

All previous and study-concomitant therapies taken/administered less than or equal to 24 hours prior to randomization into the study will be recorded in the CRF. All medications administered randomization and up to 24 hours post-study drug discontinuation will also be recorded in the CRF. The generic name, start/end dates and times of administration, route, dose regimen, and indication will be recorded.

- Age > 18 yo
- Pregnancy test (-) if female in fertile age
 - Obtain Informed Consent
- Remifentanil infusion lasting > or = 5 days
 - On Pressure Support Ventilation

[figure not shown]

Fig 1. Screening Period

[figure not shown]
GROUP 1

Remifentanil iv alone

At each visit we will record:

- An Arterial Blood Gases (ABG) sample will be collected
- Glasgow Coma Scale, RASS, the dosage of remifentanil;
- Respiratory parameters: Ventilation mode, Pressure Support, Respiratory Rate, Tidal Volume, peep, FiO_2 , EtCO_2 , SpO_2 ; if spontaneously breathing: FiO_2 , RR, SpO_2
- Haemodynamic parameters

EAdi, flow and Paw waveforms will be recorded 1, 6, 12, 24 hours from the time of randomization for day 1 and every 24 hours for the following days.

Day 1

[figure not shown]
Visits every 4 hours

If $\text{PaCO}_2 > 45 \text{ mmHg}$ $\downarrow 0.025 \text{ mcg/kg/min}$
 If $\text{PaCO}_2 40-45 \text{ mmHg}$ $\downarrow 0.0125 \text{ mcg/kg/min}$
 If $\text{PaCO}_2 35-40 \text{ mmHg}$ $\approx \text{no changes}$
 If $\text{PaCO}_2 30-35 \text{ mmHg}$ $\uparrow 0.0125 \text{ mcg/kg/min}$
 If $\text{PaCO}_2 < 30 \text{ mmHg}$ $\uparrow 0.025 \text{ mcg/kg/min}$

Day 2 and 3

Visits every 6 hours

If $\text{PaCO}_2 > 45 \text{ mmHg}$ $\downarrow 0.025 \text{ mcg/kg/min}$
 If $\text{PaCO}_2 30-45 \text{ mmHg}$ $\downarrow 0.0125 \text{ mcg/kg/min}$
 If $\text{PaCO}_2 < 30 \text{ mmHg}$ $\uparrow 0.0125 \text{ mcg/kg/min}$

GROUP 2

Starts TTS fentanyl 50 mcg/hr and maintain remifentanil iv

[figure not shown]
EVERY 24 HOURS

- If $\text{PaCO}_2 > 45 \text{ mmHg}$ remove TTS-fentanyl 25 mcg/hr
- If $\text{PaCO}_2 35-45 \text{ mmHg}$ don't add or remove tts fentanyl
- If $\text{PaCO}_2 30-35 \text{ mmHg}$ add TTS-fentanyl 50 mcg/hr
- If $\text{PaCO}_2 < 30 \text{ mmHg}$ add TTS-fentanyl 75 mcg/hr

At each visit we will record:

- An Arterial Blood Gases (ABG) sample will be collected
- Glasgow Coma Scale, RASS, the dosage of remifentanil and TTS-fentanyl;

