- Respiratory parameters: Ventilation mode, Pressure Support, Respiratory Rate, Tidal Volume, peep, FiO_2 , EtCO_2 , SpO_2 ; if spontaneously breathing: FiO_2 , RR, SpO_2
- Haemodynamic parameters

4 Hours

Day 1
Visits every 4 hours

- If $\text{PaCO}_2 > 45 \text{ mmHg}$ $\downarrow 0.025 \text{ mcg/kg/min}$
- If $\text{PaCO}_2 40-45 \text{ mmHg}$ $\downarrow 0.0125 \text{ mcg/kg/min}$
- If $\text{PaCO}_2 35-40 \text{ mmHg}$ \approx no changes
- If $\text{PaCO}_2 30-35 \text{ mmHg}$ $\uparrow 0.0125 \text{ mcg/kg/min}$
- If $\text{PaCO}_2 < 30 \text{ mmHg}$ $\uparrow 0.025 \text{ mcg/kg/min}$

Day 2 and 3
Visits every 6 hours

- If $\text{PaCO}_2 > 45 \text{ mmHg}$ $\downarrow 0.025 \text{ mcg/kg/min}$
- If $\text{PaCO}_2 30-45 \text{ mmHg}$ $\downarrow 0.0125 \text{ mcg/kg/min}$
- If $\text{PaCO}_2 < 30 \text{ mmHg}$ $\uparrow 0.0125 \text{ mcg/kg/min}$

EAdi, flow and Paw waveforms will be recorded 1, 6, 12, 24 hours from the time of randomization for day 1 and every 24 hours for the following days.

Figure 3. Treatment Period Group 2

[figure not shown]

Figure 4. Study Design

Screening Period	Verify inclusion/exclusion Criteria, Obtain Pregnancy test and Informed consent
Patient Enrolled	Baseline: ABG sample, respiratory and hemodynamic parameters, GCS, RASS, dosage of remifentanil at inclusion, 1-hour recording of EAdi, flow, and Paw
Treatment period	Randomization (group 1 remifentanil alone, group 2 remifentanil + TTS-fentanyl)
1 hour*	Recording of EAdi, flow, and Paw
4 hours* (Visit 1)	ABG sample, respiratory and hemodynamic parameters, GCS, RASS, dosage of remifentanil and TTS-fentanyl
6 hours*	Recording of EAdi, flow, and Paw
8 hours* (visit 2)	ABG sample, respiratory and hemodynamic parameters, GCS, RASS, dosage of remifentanil and TTS-fentanyl
12 hours* (visit 3)	ABG sample, respiratory and hemodynamic parameters, GCS, RASS, dosage of remifentanil and TTS-fentanyl, Recording of EAdi, flow, and Paw

16 hours* (visit 4)	ABG sample, respiratory and hemodynamic parameters, GCS, RASS, dosage of remifentanil and TTS-fentanyl
20 hours* (visit 5)	ABG sample, respiratory and hemodynamic parameters, GCS, RASS, dosage of remifentanil and TTS-fentanyl
24 hours* (visit 6)	ABG sample, respiratory and hemodynamic parameters, GCS, RASS, dosage of remifentanil and TTS-fentanyl, Recording of EAdi, flow, and Paw
30 hours* (visit 7)	ABG sample, respiratory and hemodynamic parameters, GCS, RASS, dosage of remifentanil and TTS-fentanyl

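### A work-of-breathing AUC that is not higher cannot by itself show that the patch replaced remifentanil, and the recorded remifentanil dose is not a named endpoint

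*Combined protocol and SAP*

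**What the plan says.** Section 4.2 starts the patch "simultaneously with the preexistent remifentanil continue infusion", so Group 2 is an add-on arm. Remifentanil is adjusted on blood gases in both arms. For Group 1, "the infusion rate will be increased or decreased according to the study protocol based on PaCO₂ value"; for Group 2, "Remifentanil infusion rate will be increased or decreased based on PaCO₂ value". The steps are in the treatment-period flow charts, and the remifentanil lines for day 1 and for days 2–3 are the same in both groups.

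Section 2.1 frames the aim as non-inferiority. Section 2.2 asks that the AUC of work of breathing per minute be not higher with the patch. No margin is given. Section 6 names a Wilcoxon-Mann-Whitney test at two-sided 0.05.

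The title is about weaning from remifentanil. The hypothesis, just before Section 2, says of the patch that "it can have a role in weaning the patient from intravenous opioids".

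On remifentanil itself, Section 2.4 lists "global duration of mechanical ventilation and intravenous remifentanil infusion". The synopsis list of secondary objectives leaves remifentanil duration out. Table 1 collects "dosage of remifentanil at inclusion" and the remifentanil dosage at each of visits 1 to 14. No endpoint in Sections 2.2, 2.4 or 2.5, and no analysis named in Section 6, uses that dosage.

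**The concern.** If the patch did nothing, Group 2 would be a second control group: same remifentanil, same rule, same expected work of breathing. The primary criterion would then be met by default. It could also be met if patients simply received extra opioid, since the criterion looks only for an increase in work of breathing. A positive primary result therefore does not separate three explanations: the patch replaced remifentanil, the patch did nothing, or the patch added to total opioid.

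The variable that bears most directly on replacement is the amount of remifentanil given. It is collected 15 times per patient and has no prespecified use. The trial could report a successful primary endpoint and leave its own hypothesis resting on infusion duration alone.

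**Working it through.** **1. The plan's own figures.** Section 6.1 takes 10 patients (read here as per group) and attrition under 10%: 10 / 0.90 = 11.1, rounded up to 12 per group and 24 in total. This reproduces. No effect size, SD, margin or power is stated, so there is no power calculation to reproduce. Section 1.3 converts 300 mcg/h of patch to 1.80 mg/day of remifentanil: 1,800 mcg / 70 kg / 1,440 min = 0.0179 mcg/kg/min (plan: 0.0178). This also reproduces.

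**2. How often the primary criterion is met.** Exact two-sided Wilcoxon-Mann-Whitney test at 0.05, 12 v 12, normal data assumed, 4,000 simulated trials:

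| True increase in AUC with patch | Not significantly higher | Observed median not higher |
|---|---|---|
| 0 (inert patch) | 98% | 50% |
| 0.5 SD | 81% | 14% |
| 1.0 SD | 41% | 2% |

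The plan does not say which reading applies. On either one, passing does not distinguish an inert patch from a working one.

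**3. What duration measures.** On days 2–3 the flow charts lower remifentanil by 0.0125 mcg/kg/min at every visit with PaCO₂ of 30–45 mmHg, in both arms. The visits are at 30, 36, 42, 48, 54, 60, 66 and 72 h, so there are 8 steps: 8 × 0.0125 = 0.10 mcg/kg/min. The last step falls at 72 h itself, so 7 × 0.0125 = 0.0875 takes effect inside the window. For a patient who stays in that band:

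- a rate of 0.05 at 24 h needs 0.05 / 0.0125 = 4 steps and stops at 24 + 4 × 6 = 48 h;
- a rate of 0.10 needs 8 steps and stops at 72 h;
- a rate above 0.10 is still running at 72 h, after which Section 4.4 leaves treatment to the investigator. No blinding is described.

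Duration therefore depends partly on the starting rate in either arm, and it does not register a lower rate over the same hours.

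**4. How much replacement to expect.** Scaling Section 1.3's conversion linearly (an assumption):

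- starting patch dose, 50 mcg/h: 0.0179 × 50/300 = 0.0030 mcg/kg/min;
- highest level the flow chart's 24-hour steps reach before 72 h (50, then 125, then 200 mcg/h): 0.0179 × 200/300 = 0.0119 mcg/kg/min.

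Both are below the smallest remifentanil step, 0.0125. On the plan's own figures the difference in dose may be small.

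**5. What 12 per arm can say about dose.** The 95% CI half-width is t(0.975, 22) × √(2/12) = 2.074 × 0.408 = 0.85 SD. The noncentral t gives 80% power for a difference of 1.20 SD, or 1.32 SD with 10 evaluable per arm. The documents give no SD for dose, so these cannot be put in mcg/kg.

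**The case against.** The strongest reply has four parts.

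- **The stated primary objective is work of breathing, not remifentanil sparing, and this is a 24-patient pilot.** That is so. It argues for secondary status and estimation, not for leaving dose out.
- **Remifentanil is not unmeasured.** Infusion duration is a secondary objective and endpoint (Sections 2.3 and 2.4), and Section 6 applies a rank test to quantitative variables in general. This stands. A reader might infer that the trial has no remifentanil outcome, or that dose could never be compared. The documents do not support either; what is missing is a prespecified dose endpoint.
- **The titration does not fix the AUC.** A reader might infer that a common PaCO₂ rule holds work of breathing equal for the full 72 hours. The day 1 table, with its no-change zone at 35–40 mmHg, works somewhat like that. The days 2–3 table is a taper across 30–45 mmHg, under which the arms can separate, and it covers 48 of the 72 hours. The point does not need that inference: an inert patch gives equal expected AUCs under any common rule.
- **Dose is rule-driven too.** On days 2–3 it departs from the common taper only when PaCO₂ falls below 30 or rises above 45 mmHg (or the rate reaches zero). The finer bands apply on day 1, before the patch reaches full effect (12 to 24 h, Section 1.2). This stands, and it is why dose should be read with PaCO₂ and work of breathing.

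**Conclusion.** The point holds and is of moderate weight. A not-higher AUC, with no margin and an add-on arm, is the expected result even from an inert patch (about 98% of trials if read as not significantly higher; this assumes normal data and 12 evaluable per arm). It cannot by itself support the claim that the patch replaced remifentanil. Duration is a partial substitute, and the more direct variable is collected but not named as an endpoint.

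Three stronger readings should be avoided:

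- That a not-higher AUC should count only if remifentanil dose is significantly lower. With a CI half-width near 0.85 SD and a patch equivalent below one remifentanil step on the plan's own conversion, even a working patch would rarely meet that.
- That the days 2–3 taper can be run forward to predict when higher rates stop. It is written for those two days only.
- That baseline adjustment brings a known gain in precision. The documents give no distribution of starting rates or PaCO₂, so its size cannot be stated.

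**What to change.** 1. In Sections 2.4 and 6, and in the synopsis, add remifentanil dose over 0–72 h as a secondary endpoint. Use either the cumulative dose in mcg/kg (sum of rate × minutes between visits) or its time-weighted mean. Say whether the rate recorded at a visit is the one before or after that visit's adjustment.
2. Report the between-arm difference with a 95% CI, adjusted for remifentanil dose at inclusion. Adjust infusion duration for the same baseline value.
3. State how patients are handled who die or withdraw before 72 h. Section 7 counts both as withdrawn, and a truncated total would look like a low dose. Patients who have come off remifentanil contribute a rate of zero.
4. In Section 2.1, state that a not-higher AUC alone does not show remifentanil replacement and is to be read alongside the dose estimate and PaCO₂, without requiring a significantly lower dose.

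The cost is a few lines of text and one derived variable. The data are already in the visit schedule, N stays at 24, and no change to titration is proposed. The downside is a more modest conclusion, with a dose comparison that estimates and does not confirm.
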